1. OBJECTIVES

Our study objective is to determine whether contrast enhanced spectral mammography (CESM) can predict which cases of atypical ductal hyperplasia (ADH) diagnosed at core needle biopsy will upgrade to breast malignancy at the time of surgical excision.

Hypothesis: CESM can reliably predict which cases of ADH will upgrade to malignancy at the time of surgical excision.

1.1 Study Design

This is a prospective clinical pilot study evaluating whether CESM can predict upgrade rates to malignancy at the time of surgical excision. All study participants with a diagnosis of ADH on core needle biopsy, who will be getting subsequent surgical excision, will have a CESM prior to surgical excision. CESM outcomes will be compared with the surgical outcomes to determine whether CESM can predict upgrade to malignancy.

Study Population: Women \geq 30 years of age with a diagnosis of ADH identified by ultrasound and stereotactic core biopsy who will be getting subsequent surgical excision will be included in this study.

Recruitment and Enrollment: No formal publicity of the research study will be performed. Subjects will be approached for study participation by a research coordinator after their diagnosis of ADH and completed diagnostic work-up for this diagnosis. Interested subjects will then be enrolled in the study.

Image acquisition: CESM will be performed according to BIDMC clinical protocols for image acquisition. Omnipaque 350 (the standard CT contrast agent) will be used at a dose of 1.5 mL of contrast per kilogram of body weight at an injection rate of 3 mL/second to a maximum in dose of 150 ml. The patient's weight will be confirmed with measurement on a scale by the technologists, as is done in clinical practice, and documented on both clinical forms and case report forms.

Image interpretation: Two radiologists will independently interpret the CESM exam. Radiologists will have access to all the pertinent prior history and routine imaging. Each radiologist will document their interpretation of the biopsy site and up to 2 additional findings per exam using the Breast Imaging-Reporting and Data System (BI-RADS). The radiologist will also provide a BI-RADS code for the overall exam. If there is a discrepancy in interpretation for any finding, then a third radiologist will be the tie-breaker. The description of the site of atypia will be excluded from the clinical report and will be entered into a research note to be included in the online medical record. This will ensure that the surgeon will not be biased by the CESM interpretation of the area of atypia. In addition, all individual and final interpretations will be documented in the case report forms. Incidental findings identified on CESM (defined by >2 cm away and distinct from the biopsied mass) will be managed according to standard of care.

Pathology: Two pathologists will review the percutaneous biopsy specimen and the excisional biopsy specimen and provide independent interpretations regarding the presence/absence of

ADH, DCIS, and invasive cancer. If there is disagreement, a third pathology will be the tie-breaker. Final pathology will be recorded on the case report form as well as the online medical record.

Surgical Management: The presumed initial surgical treatment plan will be recorded based on the imaging findings at the time of diagnostic imaging. The final surgical treatment will also be recorded.

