5. TREATMENT AND/OR IMAGING PLAN

The CESM exam will be performed according to clinical protocol. Omnipaque 350 (the standard CT contrast agent) will be administered at a dose of 1.5 mL of contrast per kilogram of body weight at an injection rate of 3 mL/second, according to clinical protocol. Images will be acquired within approximately 2-12 minutes of contrast injection. A low energy and high energy image will be acquired of each breast in two projections for a total of four images per breast. The voltage will be based on breast tissue thickness and will conform to the Mammography Quality Standards Act guidelines for quality control. The total radiation dose of CESM has been shown to be approximately 20-80% greater than the dose of a standard mammogram (11,12). Please see 1.1 above for the detailed study design.

A clinical report will be generated and entered into the online medical record. The description of the site of atypia will be excluded from the clinical report and will be entered into a research note to be included in the online medical record. This will ensure that the surgeon will not be biased by the CESM interpretation of the area of atypia.

All incidental areas identified on the CESM study (>2cm away and distinct from the biopsied mass) will be managed according to standard of care.

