9.1.2 Methods for Evaluation of Disease on CESM

Two radiologists will prospectively review the CESM, and will use a third as tie-breaker. The CESM will be evaluated for the biopsy site and up to two additional findings in either breast. The biopsy site will be evaluated for abnormal findings that would suggest malignant involvement such as abnormal enhancement around the biopsy site, abnormal calcifications or masses. The result of the consensus will be documented in the clinical

report.

All measurements should be taken and recorded in metric notation using a digital measurement tool. A BI-RADS code will be assigned to each finding. This code provides a probability of malignancy score as well as a management recommendation.

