9.1.3 Methods for Evaluation of Disease on Pathology

Each biopsy and surgical excision specimen will be reviewed by two pathologists independently to determine the presence of malignancy. If there is a discrepancy, then a third pathologist will be the tie-breaker.

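### No masking to CESM is stated for the pathologists who set the reference standard, and the plan conflicts on whether the site-level CESM read stays out of the clinical report

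*Combined protocol and SAP*

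**What the plan says.** On the CESM read:

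- Section 1.1: each participant "will have a CESM prior to surgical excision". Section 9.1.2: "Two radiologists will prospectively review the CESM, and will use a third as tie-breaker".
- Section 5, repeating 1.1: "The description of the site of atypia will be excluded from the clinical report". The site read "will be entered into a research note to be included in the online medical record". The reason given is: "This will ensure that the surgeon will not be biased by the CESM interpretation of the area of atypia".
- Section 1.1 also provides that "all individual and final interpretations will be documented in the case report forms".
- Section 9.1.2, which describes how the biopsy site is evaluated, says that the consensus result is documented in the clinical report.
- Section 11.1 adds an overall BI-RADS code for each exam, set by its most suspicious finding.

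On pathology:

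- Section 9.1.3: "Each biopsy and surgical excision specimen will be reviewed by two pathologists independently to determine the presence of malignancy". A third pathologist breaks ties. Section 1.1 gives the same arrangement and adds: "Final pathology will be recorded on the case report form as well as the online medical record".
- Section 11.1: positive truth is DCIS or invasive cancer on final pathologic review. The primary outcome sets the CESM code of the biopsy site against that result.

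Neither section says that any pathologist is masked to CESM.

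**The concern.** The primary comparison is sound only if the pathology call is made without knowledge of the CESM call. The plan recognises that knowing the CESM read can influence a clinician, yet its only safeguard is aimed at the surgeon. For the pathologists, independence in context means independence of each other, not of the imaging.

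The site read is to be filed in the record system that also receives final pathology. Under 9.1.2 it may appear in the clinical report as well. If knowledge of a suspicious CESM makes a malignant call more likely on a doubtful specimen, the reference standard partly contains the index test. Such re-calls raise apparent sensitivity, specificity and PPV together, and raise the chance of rejecting the null when CESM carries no information. With about 6 malignant cases expected, one or two calls can change the result, and section 2.2 says that the result will drive a larger study.

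**Working it through.** **1. Who is protected, and when the read exists**

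| Step | Section | What is stated |
|---|---|---|
| CESM performed | 1.1 | Before excision |
| CESM read | 9.1.2 | Prospectively |
| Site read filed | 1.1, 5 | Research note in the online record, not in the clinical report |
| Consensus filed | 9.1.2 | Clinical report |
| Protected from the read | 1.1, 5 | Surgeon |
| Excision reviewed | 1.1, 9.1.3 | Two pathologists and a tie-breaker; no masking stated |

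The note is not dated. That it can exist before pathology review is an inference from the first two rows and from the aim of protecting the surgeon, which has a purpose only if the read exists before surgery.

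**2. The plan's own sample size**

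Inputs from sections 11 and 11.2: two-sided 0.05, power 0.9, sensitivity 0.9, specificity 0.8 (so 0.2 positive among benign), upgrade rate 0.2. The plan names no test. Exact power of the two-sided Fisher test is 0.868 for 5 + 20 and 0.920 for 6 + 24. The second is the smallest 1:4 design to reach 0.9, so N = 30 is reproduced. Expected positives are 6 × 0.9 = 5.4 and 24 × 0.2 = 4.8 (printed as 5.5 and 5). The overall positive rate is 0.2 × 0.9 + 0.8 × 0.2 = 0.34.

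**3. Effect of a few re-calls on the expected table**

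Move j benign CESM-positive cases to malignant. Sensitivity = (5.4 + j)/(6 + j), specificity = 19.2/(24 − j), PPV = (5.4 + j)/10.2.

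| j | Sensitivity | Specificity | PPV |
|---|---|---|---|
| 0 | 0.90 | 0.80 | 0.53 |
| 1 | 0.91 | 0.83 | 0.63 |
| 2 | 0.93 | 0.87 | 0.73 |

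**4. Effect on the test in a weaker table**

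Fisher's two-sided p for 3/6 against 5/24 positive is 0.30. One re-call gives 4/7 against 4/23, p = 0.060. Two give 5/8 against 3/22, p = 0.016.

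**5. False rejection when CESM has no value**

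Assumptions: N = 30; each woman truly malignant with probability 0.2; CESM positive in 34% whatever the truth; Fisher's two-sided test at 0.05; a fraction q of all benign CESM-positive final calls changed to malignant. The documents give no value for q.

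| q | Probability of rejection |
|---|---|
| 0 | about 2% |
| 10% | about 6% |
| 20% | about 12% |
| 30% | about 22% |

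If re-calls run in both directions (discordant malignant cases also changed to benign, starting from 6 + 24), 10%, 20% and 30% give 6.9%, 17.9% and 35.8%.

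**6. If readers err independently**

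A final call needs two of three readers. If each re-calls independently with probability r, the final rate is 3r² − 2r³. With r = 0.10 this is 0.030 − 0.002 = 0.028, and false rejection is about 3%, below the nominal 5%. A final rate of 10%, 20% or 30% would need r of about 20%, 29% or 36%. The larger figures in step 5 therefore require a bias that the readers share.

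**The case against.** Four points can fairly be made against this.

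- *Silence is not exposure.* A reader might infer that the pathologists will see the CESM read before they sign out the excision. The documents do not say that. They do not date the note, and they do not say that a pathologist opens it. A shared record system shows opportunity only. This stands, and it limits the point to a missing safeguard.
- *Two readers and a tie-breaker already protect truth.* They do against independent error, as step 6 shows. They do not protect against a bias common to readers who can see the same note or report. It is also tempting to read the tie-breaker as an admission that the ADH/DCIS call is unstable. The plan uses the same device for conventional imaging and for CESM, so it does not show that.
- *The size rests on assumptions.* Fisher's test and the re-call rates are not in the plan. A 10% rate applied to every benign CESM-positive case gives only about 6%, close to nominal. The shifts in sensitivity and specificity are small, and section 11.2 says that accuracy measures are not primary objectives at this sample size. All of this stands.
- *The note may serve the patient's record.* The analysis does not need it, because every read is on the case report form, but that does not make it useless in the chart. This stands as a reason to delay the note rather than abolish it.

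**Conclusion.** The point holds as a gap in design together with an internal conflict. The plan protects the surgeon from the site-level CESM read and states no protection for the pathologists who define truth. Section 9.1.2 contradicts 1.1 and 5 on whether the consensus read enters the clinical report, which would be a more direct route to it than the research note. The read can be available at pathology review; that rests on inference about timing. Bias in the reference standard is possible and is not shown.

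The size is conditional. False rejection goes from about 2% to 6%, 12% or 22% if 10%, 20% or 30% of benign CESM-positive final calls were changed by a shared bias, with Fisher's test and a CESM of no value. It stays near 3% if readers err independently at 10% each. A reader should not conclude that the trial's result will be biased, nor that its sample size is wrong. The change is worth making because it guards the primary comparison at little cost.

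**What to change.** 1. In 1.1 and 9.1.3, state that all study pathologists, including the tie-breaker, read the excision specimen masked to CESM images, codes and notes.
2. In 1.1 and 5, keep the site-level read on the case report form and in RedCap, and release the research note to the online record only after final excision pathology is locked.
3. Reconcile 9.1.2 with 1.1 and 5, so that before that lock the clinical report carries neither the site-level consensus nor an overall BI-RADS code driven by the site. The documents do not say whether the overall code goes into the clinical report; the amended text should. The provision for incidental findings distinct from the biopsied area is not affected.

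The cost is protocol wording and a later posting date. N stays at 30 and no readers are added. The downside is that the site read reaches the chart later. If the note must stay in the chart, the masking statement in item 1 alone removes most of the risk, and item 3 is still needed because the sections contradict each other.

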1.2 Primary Objectives

To determine whether CESM can predict upgrade rates of biopsy proven ADH at surgical excision

1.3 Secondary Objectives

To evaluate how CESM impacts surgical management of patients diagnosed with ADH

2. BACKGROUND

2.1 Study Disease(s)

Atypical ductal hyperplasia (ADH) is a common pathology result after percutaneous breast biopsy. Although not malignant itself, ADH is viewed as a precursor lesion to breast cancer. The literature reports highly variable upgrade rates of ADH to breast cancer (1-4). As a result, the standard of care is to perform surgical excision on all patients with this diagnosis at biopsy to identify potential cancer.

2.2 Rationale

Preliminary attempts to identify those cases of ADH that will upgrade to cancer using breast MRI has been performed and has shown promise (5-9). CESM is an imaging tool that uses a dual energy technique after contrast administration to identify breast cancer. The exam provides two sets of images for interpretation. One set has the appearance of conventional mammographic images and the other highlights areas of contrast uptake, similar to breast MRI. As a result, a CESM provides information on both morphology/density and vascularity, without the need for breast MRI. This is beneficial as CESM is a lower cost, faster, more universally accessible exam than MRI given that it is an add-on unit to conventional mammography equipment.

Our objective is to perform a preliminary study to determine whether we can predict upgrade of atypia to malignancy using CESM. The results of this study will drive a larger study on the role of CESM in this setting.

3. PARTICIPANT SELECTION

Given that this study involves an FDA approved imaging test that is used in clinical care with a well-established risk profile, and does not involve a therapeutic agent or investigational device, informed consent will be performed by any member of the study team, including the study

coordinator.

3.1 Eligibility Criteria

3.1.1 Women

3.1.2 Age, Minimum 30 years. CESM is an imaging exam that uses radiation and is not typically employed in women younger than age 30 due to potentially negative biologic effects on glandular breast tissue.

3.1.3 Participants who had a percutaneous breast biopsy (to include stereotactic, tomosynthesis, or ultrasound guided) that revealed ADH

3.1.4 Participants will be undergoing surgical excision to remove the ADH.

3.1.5 Participants must have normal organ and marrow function as defined by a GFR ≥ 60 mL/min/1.73 m² to be performed per clinical protocol.

CLINICAL PROCOTOL USED AS REFERENCE FOR THIS STUDY:

(i) Patients ≥ 65 years without underlying renal insufficiency get GFR tested within 6 months of the exam.

(ii) Patients < 65 years without underlying renal insufficiency do not require an GFR calculation)

(iii) Patients ≥ 65 years with known underlying renal insufficiency get GFR tested within 1 month of the exam.

(iv) Patients < 65 years with known renal insufficiency get GFR tested within 1 month of the exam.

3.1.6 Because of the potential teratogenic effects of radiation, women of child-bearing potential must agree to use adequate contraception (hormonal or barrier method of birth control; abstinence) prior to study entry, until the CESM is performed. Should a woman become pregnant or suspect she is pregnant, she should inform the study team prior to getting the CESM.

3.1.7 Ability to understand and the willingness to sign a written informed consent document.

3.2 Exclusion Criteria

- 3.2.1 Participants with a core biopsy diagnosis of atypia with associated malignancy (in the same quadrant) will be excluded.
- 3.2.2 Participant had a breast MRI that was performed after the diagnosis of ADH but before surgical excision
- 3.2.3 Participants who have a known allergy to contrast media.
- 3.2.4 Participants who have a known severe allergic response to one or more allergens, as defined by anaphylaxis.
- 3.2.5 Participants with persistent asthma as defined by the National Heart, Lung, and Blood Institute.
- 3.2.6 Participants with renal insufficiency or failure, as determined by a point of care renal function blood test.
- 3.2.7 Participants who are breastfeeding are excluded because there is an unknown but potential risk for adverse events in nursing infants secondary to contrast administration in the mother.
- 3.2.8 Participants with the following underlying medical conditions: multiple myeloma, myasthenia gravis, dysproteinemias, severe cardiac disease, aortic stenosis, primary pulmonary hypertension, cardiac arrhythmia, or severe cardiomyopathy. These underlying medical conditions may make the participant more likely to develop a contrast reaction. This is based on the ACR contrast manual version 10.3 and hospital policy.
- 3.2.9 Participants with thyroid carcinoma or thyroid disease for whom systemic radioactive iodine therapy is part of planned diagnostic work-up or treatment within 2 months following the contrast mammogram study.
- 3.2.10 Participants with a concurrent active illness including, but not limited to, symptomatic congestive heart failure, unstable angina pectoris, cardiac arrhythmia, thyroid storm.
- 3.2.11 Pregnant women are excluded from this study because CESM uses radiation with the potential for teratogenic or abortifacient effects. This will be defined by a urine pregnancy test prior to the CESM study.

3.3 Inclusion of Women and Minorities

Women of all races and ethnic groups are eligible for this trial.

4. REGISTRATION

4.1 General Guidelines for DF/HCC Institutions

Institutions will register eligible participants in the Clinical Trials Management System (CTMS) OnCore. Registrations must occur prior to the initiation of protocol therapy. Any participant not registered to the protocol before protocol therapy begins will be considered ineligible and registration will be denied.

An investigator will confirm eligibility criteria and a member of the study team will complete the protocol-specific eligibility checklist.

Following registration, participants may begin protocol therapy. Issues that would cause treatment delays should be discussed with the Overall Principal Investigator (PI). If a participant does not receive protocol therapy following registration, the participant's registration on the study must be canceled. Registration cancellations must be made in OnCore as soon as possible.

4.2 Registration Process for DF/HCC Institutions

DF/HCC Standard Operating Procedure for Human Subject Research Titled *Subject Protocol Registration* (SOP #: REGIST-101) must be followed.

5. TREATMENT AND/OR IMAGING PLAN

The CESM exam will be performed according to clinical protocol. Omnipaque 350 (the standard CT contrast agent) will be administered at a dose of 1.5 mL of contrast per kilogram of body weight at an injection rate of 3 mL/second, according to clinical protocol. Images will be acquired within approximately 2-12 minutes of contrast injection. A low energy and high energy image will be acquired of each breast in two projections for a total of four images per breast. The voltage will be based on breast tissue thickness and will conform to the Mammography Quality Standards Act guidelines for quality control. The total radiation dose of CESM has been shown to be approximately 20-80% greater than the dose of a standard mammogram (11,12). Please see 1.1 above for the detailed study design.

A clinical report will be generated and entered into the online medical record. The description of the site of atypia will be excluded from the clinical report and will be entered into a research note to be included in the online medical record. This will ensure that the surgeon will not be biased by the CESM interpretation of the area of atypia.

All incidental areas identified on the CESM study (>2cm away and distinct from the biopsied mass) will be managed according to standard of care.

5.1 Pre-Treatment Criteria

- 5.1.1 GFR \geq 60 per the clinical protocol. If a GFR is not available, then a point of care renal function test will be performed and reviewed on the day of the exam before the patient receives the CESM.
- 5.1.2 Negative urine pregnancy test. If the patient is of child-bearing potential, then this will be performed and reviewed on the day of the CESM before the patient receives the exam.

5.2 Duration of Follow Up

Participants will be followed until they have surgical excision for their ADH. No additional follow-up will subsequently be performed unless clinically indicated.

The de-identified imaging data may be used for future undefined research. This has been included in the informed consent document.

5.3 Criteria for Taking a Participant Off Study

Participants will be removed from study when any of the following criteria apply:

- If surgical excision is not performed within 2 years of the study.
- Withdrawal of consent for data submission
- Death

The reason for taking a participant off study, and the date the participant was removed, must be documented in the case report form (CRF).

When a participant is removed from protocol therapy and/or is off of the study, the relevant Off-Treatment/Off-Study information will be updated in OnCore.

6. ADVERSE EVENTS: LIST AND REPORTING REQUIREMENTS

Adverse event (AE) monitoring and reporting is a routine part of every clinical trial. Given that the contrast mammogram will be acquired according to standard of care technique without alterations in duration, contrast agent, or contrast type and given that the AE profile for this imaging exam is well established, we will not be capturing AEs for the purposes of analysis. We intend to only capture AEs for those patients who initiate phone calls to our department. Should a patient contact the research team, the PI or co-investigator will evaluate and decide the best management, to include referring patient to the primary care physician for further management or sending patient to the emergency department.

The following list of reported and/or potential AEs (Section 7.1) and the characteristics of an observed AE (Section 7.2) will determine whether the event requires expedited reporting **in addition** to routine reporting.

